To carry out the study, the hiker was previously registered. The researchers contacted the participants to explain the study. In addition, data on age, sex, foot number and associated diseases that prevented the completion of the route were obtained. One hour before starting the route, researchers who did not intervene in the exploration process, made registration and delivery to each hiker of two technical socks (1 Set and 1 Tierra) appropriate to the size of the foot and randomly for the right foot (RF) and left foot (LF). Likewise, it proceeded for non-technical socks (cotton), but in this case both feet wore the same type of sock. All the participants before the initial exploration had their socks put on for half an hour. The hike was low-difficulty, over a short distance [37]. The first 14.5 km were on asphalt and the last 15.1 km on dirt. The height range was 189 m and the pace was moderate, at 5 km/hour. The sample comprised 109 participants (53 men and 56 women). Two women had to give up the hike for personal reasons. Both wore technical socks.

The Table 1 explain the anthropometric characteristics of the participants and the distribution of the socks, differentiating by sex and feet.

Anthropometric variable	Total	Male	Female	
Gender		48.6%	51.4%	
Age (years)	44± 25	49± 21	36 ± 24	
Height (meters)	1.7± 0.1	1.7± 0.1	1.6± 0.1	

81.0±13.5

61.4±7.8

68.8±19.4

Table 1. Anthropometric variables, total sock distribution and sock distribution by gender.

BM	II	24.9± 3.6	26.6± 3.7	23.5± 9.1
Sock type di	istribution	Total %	Male %	Female %
LF sock	Tierra	40.4 (n=44)	35.8 (n=19)	44.6 (n=25)
	Set	29.4 (n=32)	35.8 (n=19)	23.3 (n=13)
	Cotton	30.2 (n=33)	28.4 (n=15)	32.1 (n=18)
RF sock	Tierra	29.4 (n=32)	35.8 (n=19)	23.3 (n=13)
	Set	40.4 (n=44)	35.8 (n=19)	44.6 (n=25)
	Cotton	30.2 (n=33)	28.4 (n=15)	32.1 (n=18)

Km=Kilometres, n=sample size, %=Percentage, ±=Standard deviation, kg=Kilogrammes, BMI=Body mass index, LF=Left foot, RF=Right foot.

4. Study variables

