Quantitative variables depending on whether the samples were paired or independent, Friedman's test for related samples and Kruskal-Wallis was performed for independent samples, both with Bonferroni correction for multiple testing was applied. For the qualitative variables the

chi-square or Fisher's exact test with a significance level of α = 0.05 was carried out. The variables analysed by logistic regression were quantified using the ODDS Ratio (OR). The effect size for the different variables was also calculated. First, for Kruskall-Wallis tests, the variation was between 0.443 y 0.888, and for Friedman tests, the variation was between 0.336 y 0.623. Therefore, in both cases the effect size could be considered median and high.

All p-values = 0.000 are less than 1 per 1000.

Results

After completing the first part of the hike, the most frequent dermal lesions among participants were blisters and erosions.

Table 3. Prevalence of skin, muscle and nail lesions during the 0-14.5 km of the hike by sex.

(0.14 = 1)				Fen	nale					Ma	ıle		
(0-14.5 km)		Tier	ra %	Se	et %	Cott	on %	Tier	ra %	Set	%	Cott	on %
Skin lesion	%Tt.	RF	LF	RF	LF	RF	LF	RF	LF	RF	LF	RF	LF
Blister	12.8	0.0	4.0	8.0	7.7	22.2	27.8	0.0	5.3	5.3	0.0	6.7	13.3
Erosion	2.8	0.0	0.0	0.0	0.0	11.1	5.6	0.0	0.0	0.0	0.0	6.7	0.0
(0.44.5.1)				Fer	male					Ma	ıle		
(0-14.5 km)		Tier	ra %	Se	et %	Cott	on %	Tier	ra %	Set	%	Cott	on %
Muscle lesion	%Tt.	RF	LF	RF	LF	RF	LF	RF	LF	RF	LF	RF	LF
Pain due inadequate warm	21.1	23.1	27.8	8.0	7.7	27.8	27.8	10.5	15.8	10.5	0.0	13.3	13.3
Inflammation	2.8	0.0	4.2	4.0	0.0	0.0	0.0	0.0	10.5	10.5	0.0	0.0	0.0
Muscle discomfort	1.8	0.0	0.0	0.0	0.00	0.0	0.0	5.3	5.3	0.0	0.0	0.0	0.0

Km=Kilometres, %=Percentage, Tt=Total, RF=Right foot, LF=Left foot.

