(14.5-29.0 KIII)		Tier	ra %	Set	t %	Cott	on %	Tierr	a %	Se	et %	Cott	on %
Nail lesion	%Tt.	RF	LF	RF	LF	RF	LF	RF	LF	RF	LF	RF	LF
Onychocryptosis	0.9	7.7	0.0	0.0	0.0	0.0	0.0	0.0	0.0	0.0	0.0	0.0	0.0
Subungual hematoma	1.9	0.0	0.0	0.0	0.0	6.3	6.3	0.0	0.0	0.0	0.0	6.7	6.7

Km=Kilometres, %=Percentage, Tt=Total, RF=Right foot, LF=Left foot.

In the second part of the hike, a greater variety of dermal lesions was detected. The most prevalent were blisters, erosions and reddened skin. Again, no urticaria, reddened skin, crevices, or helomas were detected with either technical sock. Differences were found between the percentage of dermal lesions among hikers wearing technical socks (21.1%) or non-technical socks (54.8%) (p-value=0.001). By gender, the percentage of women and men with dermal lesions was higher among wears of non-technical socks (women 68.8% and men 40%) than among wearers of technical socks (women 26.3% and men 15.8%) but the differences only were significant in women (p-value=0.006). Considering the sock used in each foot, in the case of women, presented more reddened skin in both RF and LF if they used cotton sock compared to the Tierra and Set (RF and LF p-values=0.023). In the case of men, they presented more blisters in the LF if they used Set sock than cotton or Tierra (p-value=0.021) and more erosion in the RF if they used cotton sock in comparison with the Tierra or Set (p-value=0.018) (Table 4). A greater variety of total muscle lesions was also detected in the second part of the hike: pain due to inadequate warm, inflammation, muscle discomfort and sprain. No differences were found between any of the muscular injuries analysed and the technical and non-technical socks neither by sex (Table 4).

Nail lesions like onychocryptosis (0.9%) and subungual hematomas (1.9%) were infrequently and developed only in the second part of the hike. No difference between any of the nail lesions analyzed and technical and non-technical socks were found. By sex, no differences were found (Table 4).

The temperature comparisons between technical and non-technical socks, regardless of distance, foot, measurement area and sex, showed significant differences. The Friedman test was performed (p value <0.005) for the comparisons between paired samples and the Kruskal-Wallis test was performed (p value <0.009) for independent samples. (Supplementary data, tables A, B).

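### Single skin-lesion types are tested only in sex-by-foot slices, although technical vs cotton is assigned to the hiker, so lesion-level findings are reported as side- and sex-specific without support.

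*Combined protocol and SAP*

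**What the plan says.** Section 3 (Study design, route description and participants) describes "delivery to each hiker of two technical socks (1 Set and 1 Tierra"), with the side randomised. For cotton, "in this case both feet wore the same type of sock". Every hiker is therefore wholly technical or wholly cotton.

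Section 6 (Statistical tests) says that for qualitative variables "chi-square or Fisher's exact test with a significance level of α = 0.05 was carried out". The Bonferroni statement, "both with Bonferroni correction for multiple testing was applied", refers to the Friedman and Kruskal-Wallis tests and not to the lesion tests.

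The Results compare technical with non-technical hikers for any dermal lesion: 6.6% vs 36.4% in the first part, and 21.1% vs 54.8% (p=0.001) in the second. Single skin-lesion types are compared across Tierra, Set and cotton, within one foot and one sex. In the second part, women "presented more reddened skin in both RF and LF if they used cotton sock compared to the Tierra and Set (RF and LF p-values=0.023"), and men had "more erosion in the RF if they used cotton sock in comparison with the Tierra or Set (p-value=0.018"). Men's left-foot blisters with Set are also reported (p=0.021). No hiker-level result for a single skin-lesion type and no sock-by-sex interaction test is given.

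**The concern.** For technical vs cotton, the foot side carries no information about exposure. Splitting each lesion type by foot and sex has three consequences.

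- One set of affected hikers can appear as two results, one per foot.
- A difference that has the same direction in both sexes and on both feet is reported only where a small cell happens to cross 0.05.
- The question a reader would ask, whether cotton wearers get more of a given lesion, is not answered for any single skin-lesion type.

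At stake are the lesion-specific statements. The any-dermal-lesion comparison is already made by hiker and is not affected.

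**Working it through.** **Inputs.** The denominators come from Table 1 and from the Table 4 percentages. Women: 13 technical hikers with Tierra right/Set left and 25 with Set right/Tierra left. Men: 19 and 19. Technical total: 13+25+19+19 = 76. Cotton men: 15. Cotton women: 18 at the start, but 16 in Table 4 (18.8% = 3/16; 3/18 would be 16.7%).

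**Reproducing the printed p-values.** Pearson chi-square, Σ(O−E)²/E, 2 df, three socks within one foot and sex:

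- Women, reddened skin, right foot: 0/13, 0/25, 3/16. Expected events are 0.72, 1.39 and 0.89; chi-square 7.544, p=0.0230. The left foot gives the same. Printed: 0.023.
- Men, erosion, right foot: 0/19, 0/19, 3/15. Chi-square 8.056, p=0.0178. Printed: 0.018.

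The arithmetic is right. Each result rests on three affected feet, with smallest expected counts of 0.72 and 0.85. The exact three-group test gives 0.034 and 0.019.

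**The total column counts hikers.** Heloma in men is one right and one left foot, yet the total is 0.9% = 1/107.

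**Recovering hiker counts, second part.**

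- Reddened skin: 3.7% of 107 = 4 hikers. The cells need at least 3 cotton women and 1 cotton man, already 4. So the three right feet and three left feet in women belong to the same three women. Split: 4/31 vs 0/76.
- Erosion: 7.5% of 107 = 8 hikers. The cells need at least 3 cotton women (right 2, left 3), 3 cotton men (right 3, left 2) and 2 technical women (Set right 2). 3+3+2 = 8, so the split must be 6/31 vs 2/76. The two men with left-foot erosion are among the three with right-foot erosion.
- Blisters: 19.6% of 107 = 21 hikers. Cotton women number 4 to 6 and cotton men 1, so cotton is 5 to 7 and technical 16 to 14.

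**First part.** Any dermal lesion in technical hikers is 6.6% of 76 = 5, all blisters, since no technical foot has erosion. Blisters total 12.8% of 109 = 14, leaving 14−5 = 9 in cotton. Erosion is 2.8% of 109 = 3, all cotton.

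**Hiker-level results**, two-sided Fisher, sexes pooled:

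| Lesion | Cotton | Technical | p |
|---|---|---|---|
| Blister, first part | 9/33 | 5/76 | 0.010 |
| Erosion, first part | 3/33 | 0/76 | 0.026 |
| Erosion, second part | 6/31 | 2/76 | 0.007 |
| Reddened skin, second part | 4/31 | 0/76 | 0.006 |
| Blister, second part | 5–7/31 | 16–14/76 | 0.60–1.0 |

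Newcombe interval for second-part erosion: d = 0.1935−0.0263 = 0.1672. Wilson limits are 0.0919 to 0.3628 (cotton) and 0.0073 to 0.0910 (technical).

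- Lower: 0.1672 − √[(0.1935−0.0919)² + (0.0910−0.0263)²] = 0.047.
- Upper: 0.1672 + √[(0.3628−0.1935)² + (0.0263−0.0073)²] = 0.338.

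Reddened skin, by the same method: 12.9 points (3.8 to 28.9). Second-part blisters: −4.9 points (−18.7 to 13.3) with 5 cotton cases, and 4.2 points (−10.9 to 22.8) with 7.

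**What changes the p-value: unit or pooling?** By hiker within sex, Fisher gives:

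- Erosion: men 3/15 vs 0/38, p=0.019; women 3/16 vs 2/38, p=0.15.
- Reddened skin: women 3/16 vs 0/38, p=0.023; men 1/15 vs 0/38, p=0.28.

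These barely differ from the printed slices. The fall to 0.007 and 0.006 comes mainly from pooling the sexes. A sex-stratified exact test gives the same 0.007 and 0.006. Exact tests of sock-by-sex homogeneity give p=0.45 (erosion) and 1.0 (reddened skin).

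**Multiplicity.** Six types × two feet × two sexes is 24 skin tests in the second part. If they were independent, the chance of at least one false positive would be 1−0.95²⁴ = 0.71, an upper guide because the tests are sparse and correlated. One hiker-level test per type and section makes 12; 0.05/12 = 0.0042, and none of the four p-values below 0.05 passes.

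**Denominator conflict.** Section 3 says "The sample comprised 109 participants (53 men and 56 women). Two women had to give up the hike for personal reasons", and then "Both wore technical socks". Table 4 keeps 38 technical women and drops cotton women from 18 to 16. With 33 cotton and 74 technical and the same events, p is 0.010 (erosion) and 0.008 (reddened skin).

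**The case against.** The foot-level tests compare three sock models, and technical hikers wear a different model on each foot, so that comparison has to be made by foot. Using one foot per hiker also avoids clustering within the hiker. Technical vs cotton is already tested by hiker for any dermal lesion. The text lists the strata that crossed 0.05; it does not say that erosion is confined to men's right feet, claim an interaction, or call the two feet independent confirmations. No printed contrast reverses.

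Much of this stands. The gap is limited to single skin-lesion types, since muscle and nail lesions do have a technical vs non-technical statement. Foot-level data are proper for Tierra vs Set. But the reddened-skin and erosion statements are about cotton against both technical socks, which is the hiker-level question. With no pooled result beside them, a reader will take them as side- and sex-specific.

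Two stronger readings are tempting. A reader might infer that testing by foot is what hid the effect; the within-sex hiker results show otherwise. A reader might also infer a general cotton effect on all skin lesions; the second-half blister counts do not support that.

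**Conclusion.** The point holds for single skin-lesion types. One group of three women is shown as two results, and erosion is presented as a men's right-foot finding although the other foot and the other sex have the same direction. No sock-by-sex interaction is tested or evident, though with 4 to 8 affected hikers a homogeneity test has little power.

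By hiker, cotton exceeds technical by 16.7 points for second-half erosion and 12.9 points for reddened skin, with first-half blister and erosion in the same direction. Second-half blisters show no difference, with wide intervals, so the evidence is lesion-specific. All these p-values are unadjusted and derived after the data were seen. They are no more than exploratory.

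The result assumes that the total column counts hikers and that the denominators are those the percentages imply. The conflict over the two withdrawals does not change the conclusion.

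**What to change.** - For technical vs cotton, report every skin-lesion type once per section by hiker (affected on either foot), stratified by sex, with a risk difference and 95% CI. Include second-half blisters and the rare types.
- State a multiplicity correction for this family, or label it exploratory.
- Keep the sex-by-foot cells as description without p-values, and withdraw the side- and sex-specific technical vs cotton statements.
- Analyse Tierra vs Set separately as a paired within-hiker contrast among technical hikers. The men's left-foot Set blister finding belongs there.
- Reconcile section 3 with Table 4 on which group lost the two women, and print the denominators.

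The cost is one small table from data already held. The downside is that the side-specific p-values are lost and, under a strict correction over 12 tests, none of the four lesion-level results would be called significant.

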None of the other dermal lesions included in the evaluation (reddened skin, urticaria, crevice and heloma) were detected. Significant differences were found between the percentage of dermal lesions in hikers wearing technical socks (6.6%) and non-technical socks (36.4%) (p-value=0.000). The women had a higher percentage of dermal lesions (23.2%) than the men (7.5%) (p-value=0.034), regardless of sock type. Moreover, the percentage of women with dermal lesions was significantly higher among wearers of non-technical socks (50%) than in wearers of technical socks (10.5% had lesion) (p-value=0.002). Particularly the women presented more blisters in both RF and LF when they wore cotton sock compared to the Tierra and Set socks (RF p-value = 0.050, LF p-value = 0.042). In the case of men, there was no difference in any of the skin lesions at 14.5 km on any foot compared to the sock used (Table 3). The most frequent muscle lesions at the end of the first part of the hike were pain due inadequate warm (21.1%), inflammation (2.8%) and muscle discomfort (1.8%). No sprains or nail disorders were detected at the end of the first part of the hike. No difference between any of muscle lesions analyzed and technical and non-technical socks were found. By sex, no differences were found regarding technical and non-technical socks or concerning the model used sock on each foot (Table 3).

Table 4. Prevalence of skin, muscle and nail lesions during the 14.5-29.6 km of the hike by sex.

(14.5-29.6 km)				Fema	ale					N	I ale		
(14.5-29.6 KM)		Tie	rra %	Set	%	Cott	on %	Tier	ra %	Se	et %	Cott	on %
Skin lesion	%Tt.	RF	LF	RF	LF	RF	LF	RF	LF	RF	LF	RF	LF
Blister	19.6	7.7	12.0	20.0	7.7	25.0	12.5	5.3	0.0	5.3	21.1	6.7	0.0
Erosion	7.5	0.0	4.0	8.0	0.0	12.5	18.8	0.0	0.0	0.0	0.0	20.0	13.3
Reddened skin	3.7	0.0	0.0	0.0	0.0	18.8	18.8	0.0	0.0	0.0	0.0	6.7	6.7
Urticaria	0.9	0.0	0.0	0.0	0.0	6.3	6.3	0.0	0.0	0.0	0.0	0.0	0.0
Crevice	0.9	0.0	0.0	0.0	0.0	0.0	0.0	0.0	0.0	0.0	0.0	6.7	0.0
Heloma	0.9	0.0	0.0	0.0	0.0	0.0	0.0	0.0	0.0	0.0	0.0	6.7	6.7
(14.5-29.6 km)			Female			Male							

		Tier	ra %	Set	t %	Cott	on %	Tier	a %	Se	et %	Cott	on %
Muscle lesion	%Tt.	RF	LF	RF	LF	RF	LF	RF	LF	RF	LF	RF	LF
Pain due inadequate warm	11.2	15.4	4.0	4.0	7.7	0.0	12.5	10.5	0.0	5.3	10.5	0.0	0.0
Inflammation	0.9	0.0	4.0	4.0	0.0	0.0	0.0	0.0	0.0	0.0	0.0	0.0	0.0
Muscle discomfort	0.9	0.0	0.0	0.0	0.0	0.0	0.0	0.0	0.0	5.3	0.0	0.0	0.0
Sprain	0.9	0.0	0.0	4.0	0.0	0.0	0.0	0.0	0.0	0.0	0.0	0.0	0.0
(14.5-29.6 km)				Fem	ale					N	Iale		

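### Three lesion p-values in the Table 4 text match three-sock chi-square tests on very sparse tables but are worded as one sock being worse than each of two others; by Fisher's exact test no named pair is below 0.05

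*Combined protocol and SAP*

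**What the plan says.** Section 6 (Statistical tests) assigns qualitative variables to a "chi-square or Fisher's exact test with a significance level of α = 0.05 was carried out". It gives no rule for choosing between the two and no pairwise step after a three-group result. Bonferroni is mentioned only for the Friedman and Kruskal-Wallis tests of quantitative variables ("both with Bonferroni correction for multiple testing was applied"). The temperature tables accordingly print Tierra-Set, Tierra-Cotton and Set-Cotton p-values.

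The Results text that accompanies Table 4 (14.5 to 29.6 km) makes three statements by sock model, each with one p-value per foot:

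- Women "presented more reddened skin in both RF and LF if they used cotton sock compared to the Tierra and Set (RF and LF p-values=0.023").
- Men: "they presented more blisters in the LF if they used Set sock than cotton or Tierra (p-value=0.021").
- Men: "more erosion in the RF if they used cotton sock in comparison with the Tierra or Set (p-value=0.018").

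No pairwise p-value for any lesion appears in the document.

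**The concern.** Each sentence picks out one sock and sets it against two named socks, while the p-value attached to it appears to come from a single test of all three. A significant three-group result does not say which pairs differ. The tables are also so sparse (three or four lesions each) that the chi-square approximation cannot be relied on.

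What is at stake is the set of conclusions about individual models, including that one technical sock (Set) gives men more left-foot blisters than cotton does. A reader would take these as established sock-against-sock differences.

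**Working it through.** **Inputs.** Group sizes come from Table 1 and percentages from Table 4. The men's erosion row is "Erosion 7.5 0.0 4.0 8.0 0.0 12.5 18.8 0.0 0.0 0.0 0.0 20.0 13.3" and the men's blister row is "Blister 19.6 7.7 12.0 20.0 7.7 25.0 12.5 5.3 0.0 5.3 21.1 6.7 0.0"; the last six figures in each are men, in the order Tierra RF, LF, Set RF, LF, Cotton RF, LF. Women's reddened skin is 0% with both technical socks and 18.8% with cotton on each foot.

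| Table | Tierra | Set | Cotton |
|---|---|---|---|
| Men RF erosion | 0/19 | 0/19 | 3/15 |
| Men LF blister | 0/19 | 4/19 | 0/15 |
| Women RF reddened skin | 0/13 | 0/25 | 3/16 |
| Women LF reddened skin | 0/25 | 0/13 | 3/16 |

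The 16 cotton women are inferred: 18.8% is 3/16, whereas Table 1 lists 18 and 3/18 would print as 16.7%.

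**Step 1: reproduce the printed p-values.** When all m lesions fall in one group of size n, out of N feet, the Pearson statistic reduces to N·m·(N−n) / [n·(N−m)]. With 2 df, p = exp(−χ²/2).

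- Erosion: 53·3·38 / (15·50) = 8.06, p = 0.0178 (printed 0.018).
- Blister: 53·4·34 / (19·49) = 7.74, p = 0.0208 (printed 0.021).
- Reddened skin, either foot: 54·3·38 / (16·51) = 7.54, p = 0.0230 (printed 0.023). With 18 cotton women it would be 56·3·38 / (18·53) = 6.69, p = 0.035.

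**Step 2: expected lesion counts (m × group size / N).** In the order Tierra, Set, Cotton: erosion 1.08, 1.08, 0.85; blister 1.43, 1.43, 1.13; reddened skin RF 0.72, 1.39, 0.89 (first two swapped on LF). All are below 1.5.

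**Step 3: exact three-group test (Freeman-Halton).** This sums the probabilities of all tables no more likely than the one observed. C(a,b) is the number of ways to choose b from a.

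- Erosion: C(15,3)/C(53,3) = 455/23426 = 0.019.
- Blister: [2·C(19,4) + C(15,4)]/C(53,4) = 9117/292825 = 0.031.
- Reddened skin: [C(16,3) + C(13,3)]/C(54,3) = 846/24804 = 0.034.

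**Step 4: the pairs that the sentences name, two-sided and unadjusted.**

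| Pair | Fisher, by counting | Fisher p | Uncorrected Pearson p |
|---|---|---|---|
| Erosion, Cotton v Tierra | 455/5984 | 0.076 | 0.041 |
| Erosion, Cotton v Set | 455/5984 | 0.076 | 0.041 |
| Blister, Set v Tierra | 2·3876/73815 | 0.105 | 0.034 |
| Blister, Set v Cotton | (3876+1365)/46376 | 0.113 | 0.058 |
| Reddened skin, Cotton v the n=25 sock (each foot) | 560/10660 | 0.053 | 0.024 |
| Reddened skin, Cotton v the n=13 sock (each foot) | (560+286)/3654 | 0.23 | 0.099 |

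Counting both feet in women, that is eight named pairs. None is below 0.05 by Fisher. Five are below 0.05 by uncorrected Pearson.

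**Step 5: cotton against the two technical socks pooled, Fisher.** Erosion: 455/23426 = 0.019. Reddened skin: 560/24804 = 0.023.

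**The case against.** **The pairwise result depends on the test.** Section 6 allows chi-square, and uncorrected Pearson puts five of the eight pairs below 0.05, including both erosion pairs. A reader who infers that no pairwise test of any kind reaches 0.05 goes too far. But uncorrected Pearson is the approximation that these counts rule out. Even if it is accepted, only the erosion claim holds against both comparators: the blister claim fails against cotton (0.058) and each reddened-skin claim fails against the n=13 sock (0.099). With Yates's correction, or with Bonferroni for three pairs, none is below 0.05. Fisher is conservative, and some less conservative tests that the plan does not name fall on either side of 0.05. For the erosion pairs, Barnard's test gives 0.046 with pooled variance and 0.083 unpooled, and Fisher mid-p gives 0.038. Unpooled Barnard also puts both blister pairs below 0.05 (0.036 and 0.044), while Boschloo's test puts none of the pairs there.

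**The eight pairs are not eight separate pieces of evidence.** Only five distinct tables lie behind them, each with three or four lesions. Failing to reach 0.05 largely reflects low power and does not show that the socks are alike. This stands.

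**The exact test changes no label of significance.** All three exact overall p-values stay below 0.05. This stands too: the documents do not support a reading that the overall differences are artefacts of the chi-square.

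**The sentences could mean cotton against technical socks together.** On that reading the erosion and reddened-skin claims are supported (0.019 and 0.023), and the women's 0.023 could itself be that pooled Fisher test. The men's printed 0.018 is not: pooled Fisher gives 0.019. The reading cannot rescue the blister claim, which sets Set against the other technical sock and cotton. Set against those two combined gives 0.013 (3876/292825), but no stated contrast groups them that way.

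**Was the test chosen to suit the result?** The hiker-level p-values 0.034, 0.002 and 0.006 match Fisher (0.0337, 0.0021, 0.0057), so one might infer that the exact test was dropped where counts were smallest. The documents do not support that. Those are 2×2 tables and the ones here are 3×2, so table shape explains the split just as well.

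**Conclusion.** The point holds in a limited form. The printed p-values match three-group chi-square tests on tables too sparse for the approximation, and the wording claims more than such a test can show. By two-sided, unadjusted Fisher tests every named pair lies between 0.053 and 0.23. What survives is that the three socks differed (exact p 0.019, 0.031, 0.034) and that cotton differed from the pooled technical socks for men's right-foot erosion and women's reddened skin. None of these allows for the many lesion-by-foot-by-sex tests.

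This rests on counts rebuilt from rounded percentages, on two-sided testing (sidedness is not stated), and on 16 cotton women. With the 18 in Table 1, the women's exact three-group p is 0.040 and the pairwise Fisher values are 0.066 and 0.25, so the conclusion is the same. The denominators still need reconciling, because section 3 says that both women who withdrew wore technical socks.

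**What to change.** Replace 0.018, 0.021 and 0.023 with the Freeman-Halton values, and use the exact test for every other lesion table in Tables 3 and 4 with an expected count below 5. Say so in section 6. Reword the three claims to state that the three socks differed, with counts (for men's right-foot erosion, Cotton 3/15, Tierra 0/19, Set 0/19), or report cotton against pooled technical socks and label it as that contrast. Name one sock as worse than another only where a pairwise exact test supports it. State the number of cotton women used in Table 4 and why it differs from Table 1.

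The cost is a re-run of the sparse lesion tables, some rewording, and slightly less favourable p-values for these three results. No new data are needed.

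### Six muscle and nail lesion results worded as no sock difference rest on one or two affected hikers; given those totals, Fisher's exact test could not have reached 0.05.

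*Combined protocol and SAP*

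**What the plan says.** Section 6 (Statistical tests) states that for qualitative variables a "chi-square or Fisher's exact test with a significance level of α = 0.05 was carried out". It does not say which test applies when, or whether tests are two-sided.

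For the first half of the hike the Results state: "No difference between any of muscle lesions analyzed and technical and non-technical socks were found". For the second half they say the same of the muscular injuries, overall and by sex, and then of the nails: "No difference between any of the nail lesions analyzed and technical and non-technical socks were found". No p-value or interval accompanies any of these statements. The document does acknowledge rarity for the nails: "Nail lesions like onychocryptosis (0.9%) and subungual hematomas (1.9%) were infrequently and developed only in the second part of the hike". It does not say that the cases were too few to compare.

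On arm sizes, Section 3 says: "Two women had to give up the hike for personal reasons. Both wore technical socks". The second-half skin results are given for "hikers wearing technical socks (21.1%) or non-technical socks (54.8%) (p-value=0.001".

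**The concern.** A non-significant test says something about the socks only if a significant result was possible. An exact test with one or two events has very few possible outcomes, and here none of them falls below 0.05. In a study whose question is whether sock type influences foot injury, a reader may take a statement of no difference as evidence that the socks are alike for that lesion. For these six lesion types the test could not have contradicted the statement. For subungual hematoma the observed pattern points as strongly against cotton as two cases can.

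**Working it through.** **1. Arm sizes.** Table 1 gives 33 cotton wearers among 109 hikers, so technical = 109 - 33 = 76. This is the first-half split. Two dropouts leave 107. The second-half skin percentages imply 16/76 = 21.1% and 17/31 = 54.8%, so 76 v 31. The dropout sentence in Section 3 implies 74 v 33. Both are carried below.

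**2. Affected hikers (Tables 3 and 4, total column).**
- First half, n = 109: muscle discomfort 1.8% = 2/109. Both are men on Tierra feet, one right and one left. A technical wearer had only one Tierra sock, so these are two different hikers.
- Second half, n = 107: onychocryptosis, inflammation, discomfort and sprain 0.9% = 1/107 each, all in technical wearers. Subungual hematoma 1.9% = 2/107, one woman and one man, both in cotton.

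**3. Which test was used.** The stated two-group skin-lesion p-values can be checked on counts back-calculated from the percentages.

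| Comparison | Stated | Fisher | Pearson | Yates |
|---|---|---|---|---|
| Women 13/56 v men 4/53, first half | 0.034 | 0.0337 | 0.0242 | 0.0467 |
| Women, first half: technical 4/38 v cotton 9/18 | 0.002 | 0.0021 | 0.0011 | 0.0034 |
| All, second half: 16/76 v 17/31 | 0.001 | 0.0011 | 0.0006 | 0.0014 |
| Women, second half: 10/38 v 11/16 | 0.006 | 0.0057 | 0.0035 | 0.0089 |

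Only two-sided Fisher matches all four.

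**4. Smallest attainable Fisher p.** With k affected hikers, n_C cotton wearers and N in total, the least probable split puts all k in cotton. Its probability, C(n_C, k)/C(N, k), is the minimum two-sided p.

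| Technical v cotton | k = 1 | k = 2 | k = 3 |
|---|---|---|---|
| 76 v 33 (first half) | 33/109 = 0.303 | (33×32)/(109×108) = 0.090 | 0.026 |
| 76 v 31 (second half, from percentages) | 31/107 = 0.290 | (31×30)/(107×106) = 0.082 | 0.023 |
| 74 v 33 (second half, from dropout sentence) | 33/107 = 0.308 | (33×32)/(107×106) = 0.093 | 0.027 |

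With one or two affected hikers no split reaches 0.05.

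**5. Sex splits.** Both first-half discomfort cases are men (38 v 15): minimum (15×14)/(53×52) = 0.076. Every other split has at most one case. For one case the second-half minimum is 15/53 = 0.283 in men, and in women 16/54 = 0.296 (or 18/54 = 0.333 on the dropout sentence). None reaches 0.05.

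**6. What the hematoma data allow.** Cotton 2/31 = 6.5%, technical 0/76; observed Fisher p = 0.082, already the minimum. Wilson limits are 1.79% to 20.72% for 2/31 and 0 to 4.81% for 0/76. Newcombe interval for the difference:
- lower: 6.45 - √[(6.45 - 1.79)² + 4.81²] = -0.2 points
- upper: 6.45 + (20.72 - 6.45) = 20.7 points

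With 2/33 v 0/74 the interval is -0.5 to 19.6. For a second-half lesion with one technical case (0/31 v 1/76), the same method gives about -7 to +10 points, cotton minus technical.

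**7. Lesions outside the six.** First-half pain (21.1%) could reach 0.05. First-half inflammation has three hikers (2.8% = 3/109), all technical, which gives p = 0.55. It could have reached 0.05 only with all three in cotton (0.026).

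**The case against.** **The result depends on the test.** Section 6 allows chi-square, and uncorrected Pearson on the hematoma table gives p = 0.025 (0.033 at 74 v 33). The second-half per-foot p-values of 0.023, 0.021 and 0.018 match Pearson, so it was used on small cells elsewhere. The dependence is real and should be stated. But the technical v non-technical p-values reproduce as Fisher, the smallest expected count for hematoma is 0.58, and a Pearson result of 0.025 would contradict the reported absence of a difference.

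**The tests may have been on pooled nail lesions.** Pooled, there are three hikers (2/31 v 1/76, p = 0.20), and that test could have reached 0.05 (minimum 0.023). No lesion-type p-value is printed, so separate tests are inferred. The sentence, however, refers to each of the lesions analyzed, not to a pooled variable.

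**A reader might infer that the null results were guaranteed before the hike, whatever the socks did.** The documents do not support this. The minima are conditional on the totals observed; a strong effect could have produced more cases and a test able to reject.

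**A reader might also assume that the sex splits always have less capacity.** That is not so: for discomfort in men the minimum is 0.076, against 0.090 overall. They still cannot reach 0.05.

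**The wording reports a non-finding and concedes that nail lesions were infrequent.** True, and Table 4 shows hematoma only in the cotton columns. This limits the seriousness, but without counts by arm or an interval the sentence still reads as a result.

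**Conclusion.** The point holds for six lesion-type results. Given the observed totals and two-sided Fisher, p could not fall below 0.29 with one affected hiker or below 0.082 (second half) and 0.090 (first half) with two. Under the dropout sentence the second-half minima are 0.31 and 0.093, so the arm conflict does not alter the conclusion. The statements of no difference for these lesions are therefore uninformative. For hematoma, a cotton excess of about 20 points is not excluded.

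This does not show that cotton causes hematomas: the interval includes zero and there are two cases. Nor does it extend to every muscle lesion, since first-half pain and inflammation could have reached 0.05, inflammation only just. The main skin-lesion and temperature results do not rest on these sentences.

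Assumptions: two-sided tests, the hiker as unit, and counts recovered from rounded percentages.

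**What to change.** - For lesion types with only a few affected hikers, drop the significance tests and their sex splits. Report counts by arm with a 95% CI for the risk difference.
- Replace the statement of no difference with one that the cases were too few to compare, and state that both subungual hematomas occurred in cotton wearers.
- Report first-half inflammation (three hikers) the same way. A strict cutoff at three would keep a test that can reject only if every case is in cotton.
- Say which test was used for each lesion comparison, and whether nail lesions were tested by type or pooled.
- Reconcile which arm the two dropouts came from: Section 3 says technical, while the second-half percentages imply cotton.

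The cost is rewording, one small table and fewer p-values to report. No new data are needed.
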